Trial Arm 1 VRT (intervention arm): VOG-based logic rules determine rapid triage pathway

- report includes direct device output (physiologic traces, quantitative measures) plus most likely diagnosis, category, and clinical trial care pathway (peripheral, equivocal, central) instructions
- the VOG results become part of the patient's clinical record

The roles of the ED provider in the care of patients in the VOG arm will be as follows:

- assess illness severity and appropriateness of the patient for VOG testing and the study protocol
- exclude obvious general medical conditions
- take over diagnostic decision-making for patients in whom VOG is equivocal (with consultant input, if available)
- intervene to deviate from VRT pathway if they are concerned about safety for patients in the VOG arm

Note: these are the same roles anticipated for ED providers if the VOG device were used for clinical practice

Trial Arm 2 Standard Care (control arm): usual ED care plus VOG exam, no VOG report generated

- no VOG automated interpretation or summary report will be generated; the computer-based randomization algorithm does not generate a VOG report or pathway using logic rules in the control (standard care) arm

The roles of the ED provider in the care of patients in the standard care arm will be as follows:

- assess illness severity and appropriateness of the patient for VOG testing and the study protocol
- exclude obvious general medical conditions
- all diagnosis, consultation, treatment, and disposition decisions will be made by the treating ED provider(s)

5.1.3 Expert Human VRT Double-Check: The VRT algorithm outputs in the intervention arm will be double-checked by expert neuro-otology fellows or faculty in real time to ensure accuracy; human judgment will “trump” VRT if there is disagreement (or if, for technical reasons, the real-time algorithm is not able to be generated – for example, as with internet connectivity problems or during development). The expert human double-check procedure will be in place at the start of the main trial, and we anticipate it will remain in place until the VRT algorithm is refined (as per pre-specified adaptations during the trial period) such that it appears accurate and safe.

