6.3.24 Resource utilization: SCs will record the number and type of brain imaging studies, consultations, and admissions, as well as ED length of stay. They will note key process measures such as whether patients are treated with anti-vertigo medications or undergo specific canalith repositioning therapy.

We will track use of higher-cost services likely to be impacted by VOG care at ED visit and in follow-up (radiology/lab tests, physician consultations, admissions). Costs will be based on national average Medicare reimbursement (commonly used in cost analyses¹⁷⁰), or, as needed, average consortium costs.

6.3.25 Medical record review: Medical records will be accessed at the ED Index Visit to identify relevant medical conditions related to inclusion/exclusion parameters or critical study covariates. SCs will review medical records for baseline medical comorbidities (and any acquired during the 30-day follow-up period), ED/hospital/outpatient healthcare visits, and major medical events (falls, hip fractures, vascular events [stroke, myocardial infarction, venous thromboembolism], and test or treatment complications related to studies/interventions during the study period (ED Index through 1-month).

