1.3 Study design

Randomized controlled trial (individual patient randomization), parallel design (1:1) (Figure 1).

Patients screened but not eligible for randomization will be enrolled in an observational arm that undergoes limited follow-up to ascertain for clinical outcomes, particularly stroke events.

Trial Arm 1 VRT (intervention arm): VOG-based logic rules determine rapid triage pathway.

Trial Arm 2 Standard Care (control arm): usual ED care plus VOG exam, no VOG report generated.

Observational arm: ED MRI VOG and six-month follow-up.

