Hypothesis 2: The VRT pathway is cost saving relative to current ED practice in diagnostic assessments.

Primary outcome 2: Total dollar costs of VRT as compared to SOC for diagnostic tests and consultations obtained during the ED index visit and hospital admission (for those admitted at the index visit). The cost for VRT arm does not include the costs of protocol safety MRIs or any tests not specified by the pathway but ordered for clinical purposes by ED providers. It does include tests ordered as part of the VRT pathway by consultants or ED providers in the “equivocal” pathway. Total costs will be calculated by multiplying fixed cost estimates (most recent year available average Medicare reimbursement in US dollars) by utilization rates for each ED index visit service tracked.

Statistical Analysis Plan 2: Analyses will include two-sample comparisons of mean and median costs. Mean of total cost between two study-arms will be compared by modified t-test with unequal variances. Median total cost between two study-arms will be compared by Wilcoxon-Mann-Whitney tests.¹⁶²

2.2.3 Aim 3 (Observational Outcome): Compare clinical outcomes for correct vs. incorrect diagnoses

Hypothesis 3: ED patients with vertigo or dizziness who receive standard care will have better outcomes if correctly diagnosed than if misdiagnosed (*this is an observational outcome in the standard-care arm*).

Primary Outcome 3: Proportion with short-term prespecified medical events of interest (PMEIs) occurring between the time of ED index visit disposition and 1-week research follow-up visit among those with correct vs. incorrect ED SOC diagnosis. “Correct” vs. “incorrect” diagnoses are categorized in one of six possible diagnosis categories (3 peripheral, 1 central, 1 medical/other, 1 non-diagnosis). PMEIs will include ED revisits, falls, vascular events (including stroke), and test or treatment complications.

Statistical Analysis Plan 3: A multivariable logistic regression will be used to estimate the odds of an PMEI (correct diagnosis vs. misdiagnosed) adjusting for demographic and clinical variables.

Specifically, define $S_i = 1$ if the i th subject experience PMEIs between the time of ED index visit disposition and 1-week research follow-up visit. Following notation used in Aim 1, define the logistic model as

$$\text{logit } P(S_i = 1 | X_{Test} = 0) = \beta_0 + \beta_1 Y_i(0) + \overline{\beta_2} \cdot \overline{Z_i}$$

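### Aim 2 compares VRT with current ED practice, but the cost of the VOG test does not reach the between-arm difference and the expert review is not a listed cost, so the comparison favours VRT by the omitted amount

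*SAP*

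**What the plan says.** SAP 2.2.2 and Protocol 9.2.2 carry the same Aim 2 text. The hypothesis is "The VRT pathway is cost saving relative to current ED practice in diagnostic assessments". The outcome is total cost of "diagnostic tests and consultations obtained during the ED index visit and hospital admission (for those admitted at the index visit"). Total cost is obtained by "multiplying fixed cost estimates (most recent year available average Medicare reimbursement in US dollars) by utilization rates for each ED index visit service tracked".

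Two exclusions are named, both for the intervention arm: "The cost for VRT arm does not include the costs of protocol safety MRIs or any tests not specified by the pathway" but ordered clinically by ED providers. No exclusion is named for the control arm.

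Protocol 6.3.24 says what is tracked: "SCs will record the number and type of brain imaging studies, consultations, and admissions, as well as ED length of stay". It adds that tracking targets the higher-cost services VOG care is likely to change, namely radiology and laboratory tests, physician consultations and admissions. Prices are Medicare averages or, as needed, average consortium costs.

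VOG is performed on all subjects before randomisation (Protocol 1.1), and SAP 1.3 defines the control arm as "usual ED care plus VOG exam, no VOG report generated". In the VRT arm only, algorithm outputs are "double-checked by expert neuro-otology fellows or faculty in real time to ensure accuracy" (Protocol 5.1.3), a step expected to take about 10 to 15 minutes per patient. Protocol 9.1 bases the primary outcome on the VRT care actually delivered, including any change the expert makes.

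**The concern.** The hypothesis and the costing rule use different comparators. The plan's own description of the control arm treats the VOG examination as an addition to usual ED care, so a comparison with current practice should set a pathway that includes VOG against one that does not. The trial gives VOG to both arms, and the costing rule does not undo this.

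The plan does correct for one research artefact: it removes the protocol safety MRI from VRT costs. The matching correction would leave VOG in the VRT arm and take the research-only VOG out of the control arm. That correction, which would raise VRT's relative cost, is not stated. The expert review raises a related problem. Accuracy is credited with the expert's contribution, while the cost comparison does not list it.

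At stake are the meaning of any declared saving and go rule (2) in SAP 2.3, which allows Phase III if accuracy is statistically equivalent and costs are lower.

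**Working it through.** **Is there a figure to reproduce?** Aim 2 states no unit cost, standard deviation, expected difference or power. The only sample size, 113 per arm, belongs to Aim 1 (90% vs 75%, alpha 0.05, power 80%). It reproduces with a continuity correction (100 per arm without) and is used below only as n.

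**Which items reach the difference?**

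| Item | VRT arm | Control arm | Listed in 6.3.24 | Reaches the VRT-minus-control difference |
|---|---|---|---|---|
| Pathway imaging, consultations, tests in the equivocal pathway | yes | as ordered | yes | yes |
| Protocol safety MRI | yes | no | excluded by name for VRT | no |
| Index VOG examination | yes | yes | no | no |
| Real-time expert review | yes | no | no | not unless read as a consultation |

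Let W be the difference in work-up cost, V the VOG cost per patient, R the cost of a review, and r the proportion of VRT patients reviewed.

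- Against current practice, with the review counted: W + V + rR.
- As written, VOG untracked: W.
- As written, VOG counted as a test obtained in both arms: W + V − V = W.

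The shortfall is c = V + rR, or c = V if the review is regarded as temporary. It always favours VRT.

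**Resources left out, from the stated times.** VOG protocol, about 20 minutes: 113 × 20/60 = 37.7 hours. Expert review: 113 × 10/60 = 18.8 to 113 × 15/60 = 28.3 hours.

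**Dollar scale.** Protocol 1.1 gives about $500M for CT, $100M for MRI, 4.4 million visits and $10 billion in total.

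- Imaging per visit: 600/4.4 = $136.
- Total per visit: 10,000/4.4 = about $2,270.
- Assumed c of $50 to $250: 50/136 = 37% and 250/136 = 183% of imaging; 50/2,270 = 2% and 250/2,270 = 11% of total.

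Neither denominator matches the outcome. The first omits consultations and tests during admission. The second includes more than diagnostic work-up. Both average over all US dizziness visits, not over patients with nystagmus or ataxia at academic-affiliated hospitals.

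As an illustration only, suppose imaging spend fell in proportion to the hypothesised drop in imaging or admission in Protocol 7 (about 50% to 15%). The saving would be 136 × (1 − 15/50) = $95, which lies inside the assumed range for c.

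**Effect on the test of means.** Assume equal standard deviations, 113 per arm, two-sided alpha 0.05, a constant c and a true full-cost difference of zero. Then SE = SD × √(2/113) = 0.133 SD, and the significance threshold is 1.96 × 0.133 = 0.26 SD. The chance of finding VRT significantly cheaper is 1 − Φ(1.96 − c/SE):

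| c (SD units) | 0 | 0.05 | 0.10 | 0.20 | 0.30 | 0.50 |
|---|---|---|---|---|---|---|
| probability | 2.5% | 5.7% | 11.3% | 32.4% | 61.6% | 96.4% |

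The documents give no standard deviation, so c cannot be placed on this scale. Exclusions under Protocol 9.1 would lower n and soften the effect somewhat.

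**When does cost decide?** Go rule (1) needs only a higher accuracy point estimate. At the planning values, SE = √(0.9×0.1/113 + 0.75×0.25/113) = 0.0496 and z = 0.15/0.0496 = 3.03, so rule (1) fails with probability of about 0.1%.

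**The case against.** The strongest reply is that nothing expressly excludes VOG or the review. The outcome covers diagnostic tests and consultations; VOG is a test, and the review could be called a consultation. Because the plan costs a pathway rather than everything received, one could also read it as charging VOG to the VRT arm alone. It stands that non-tracking is inferred from omission. But the rule prices tracked services, the list omits both items, and no sentence exempts the control arm. Simply counting VOG as a test obtained makes it cancel.

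Second, the review may be a temporary safety layer, comparable to the excluded safety MRI: Protocol 5.1.3 expects it to stay only until the algorithm appears accurate and safe. This also stands in part. Protocol 9.1 points the other way, so whether to charge the review is arguable and both results should be shown. If the central expert review of all VOG tests described for the pilot (Protocol 3) continued in the main trial, the cost of that review would fall on both arms.

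Third, Aim 2 is titled as initial diagnostic work-up cost, which could be meant to exclude the test. Hypothesis 2 is not worded that way.

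Two stronger inferences are tempting. One is that none of VRT's cost is counted. The documents do not support it: consultations, imaging and equivocal-pathway tests driven by VRT do enter, and only delivery and interpretation of the test are at issue. The other is that the omission turns a net cost into a declared saving. That would need a unit price and an expected saving, and neither is given.

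**Conclusion.** The point holds. Followed as written, Aim 2 estimates the difference in downstream work-up cost, not the net cost of VRT against current ED practice. The cost of delivering the VOG test drops out under either reading of the rule, and the expert review is not a listed cost. The bias has a known direction, in VRT's favour, and equals the omitted cost per patient.

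Its dollar size is unknown. The $50 to $250 range is an assumption, and the two denominators give very different impressions of it: small against total visit cost, large against imaging spend. A reversal of sign is possible but not shown; a large fall in the cost of admissions or consultations could outweigh the omission.

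The consequence for Phase III is limited to go rule (2). If accuracies are near the planning values, rule (1) will almost certainly settle the decision. The cost result matters there only if the accuracies turn out close, though the claim of a saving would be reported either way.

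**What to change.** In SAP 2.2.2 and Protocol 9.2.2:

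- Charge the index VOG examination to the VRT arm only, at Medicare reimbursement or, where none exists, at average consortium cost as 6.3.24 allows. Include the components that feed the algorithm, not the portable audiometry, which the schedule in Protocol 6.1 marks as time permitting.
- State that research-only VOG is not charged to the control arm.
- Report the cost difference with and without the real-time expert review, over a stated range of unit costs.
- Give the version without either item as a secondary line.

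If the sponsor prefers to leave the costing alone, restate Hypothesis 2 and go rule (2) as downstream work-up cost excluding the test itself.

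The cost is a wording change and two unit prices. VOG is given to every randomised patient, so it needs no new patient data. The documents do not say that reviews are logged, so a record of which VRT patients were reviewed should be confirmed. The downside is that the stated saving becomes less favourable to VRT.

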c) If the VOG diagnosis is *central*, the research team will request that the ED provider order a neurology consultation, neuroimaging (MRI), and admit the patient for further evaluation and testing, even if the ED provider believes the patient has a peripheral cause; a note to this effect will be placed in the patient’s medical chart as part of the research record. The ED provider will make the final decision whether to admit the patient. If the ED provider elects to discharge the patient, this would be documented as a protocol deviation. The neurology consultation may be obtained after inpatient admission, if logistical circumstances in the ED or hospital so dictate. ED providers may choose to go “off protocol” and consult an ENT physician, vestibular physical therapist, or other provider (optional) for treatment of BPPV, vestibular neuritis, or other peripheral vestibular disorder if they believe the patient has an inner ear disease.

Table 1. Assigned care pathway group and associated VRT pathway and routine clinical care events

Assigned Clinical Pathway Group	Neurology consult at ED Index Visit	ENT or PT consult at index visit	Hospital admission at ED Index Visit	Same-day MRI (for safety)	Vestibular exam (1 wk)	Research MRI (1 wk)
VOG (peripheral)	Routine	Routine	Routine	Pathway (required)	Yes	Yes
VOG (equivocal)	Pathway (required*)	Routine	Routine	Pathway (required)	Yes	Yes
VOG (central)	Pathway (required*)	Routine	Pathway (required)	Pathway (required)	Yes	Yes
Standard care	Routine	Routine	Routine	Routine	Yes	Yes

ED = emergency department; ENT = ear, nose, and throat physician; PT = physical therapist; wk = week

* The requirement for neurology consultation in equivocal cases may be waived in cases where doing so could not feasibly be accomplished within a reasonable time frame; in such a case, the ED provider would determine subsequent management without the assistance of a neurologist..

Both Trial Arms (pre-randomization & follow-up): VOG exam determines eligibility

- patient approached for consent as early as possible during ED visit; randomization occurs after VOG testing
- algorithm exam protocol (HINTS-Hallpike-Hearing) is a ~20-minute data collection in the ED by the SC
- uses commercially-available recording equipment (portable VOG device, audiometer, tablet computer)
- examination protocol is standard in neuro-otologic specialty practice
- systematic 1-week (visit), 30-day (phone, records), follow-up post randomization

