6.3.18 MRI: ED Index Visit MRIs differ from Week-1 research follow-up visit MRIs (Table 2). To maximize trial safety, all patients in the VOG arm of the study will undergo stroke protocol (safety; 1.5 Tesla) MRI with non-contrast MRA to minimize risk that a patient is erroneously discharged with a stroke. VRT-arm subjects with suspected central lesions will be admitted for stroke care and undergo clinical stroke protocol MRI with MRA as part of the required trial care pathway. VOG care patients slated for discharge will undergo same-day safety MRI if they have not had a clinical MRI. Stroke-protocol images (for safety or based on pathway VRT-C) will not be specifically adjusted or harmonized for the research study; they will use standard clinical protocols, so as to minimize clinical disruption in the ED and radiology department. Although the protocol requests a non-contrast MRI/A (to minimize total contrast dose, in light of Week-1 contrast-enhanced MRI), the patient's clinical providers may request contrast-enhanced imaging be added if clinically indicated for patients without contraindications to contrast. All enrollees will undergo a Week-1 gold-standard (3 Tesla with or without contrast) MRI (stroke, internal auditory canal sequences pre-/post-contrast, if applicable). A 1.5 Tesla basic stroke protocol MRI will be obtained if scheduling conflicts or institutional policies prevent the use of a 3T scanner. The Week-1 MRI protocol has been optimized to include images to detect posterior fossa stroke as

well as other posterior fossa and vestibular lesions (e.g., demyelinating lesions, cerebellar tumor, acoustic neuroma). The Week-1 research MRI acquisition protocol was adapted at the start of the study for each site's MRI technology (GE vs. Siemens, 3 Tesla) by the principal study neuroradiologist. The optimal MRI window is described in 6.2.3.

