 - b. Inappropriate medications (~30% standard care; hypothesized ~1% VOG)
- VII. **Risks to ED providers of medicolegal liability** [*unknown differential risk across the two arms*]

EACH OF THESE TRIAL RISKS IS DESCRIBED FURTHER BELOW

7. I. Risks of disclosure of PHI

These risks are minimal, since data security protections (described in Data and Safety Monitoring below) are in place and the data we are gathering will, in general, not be of a particularly sensitive nature.

7. II. Risks from delays in care

A theoretical risk is that clinical care will be delayed because of interference by study data collection. As in all of our previous ED-based studies,^{4,15,21,33,71-74} clinical care needs will always take precedence over our research investigations. SCs will be trained to stop their testing immediately if clinical care is needed. **There will be no delay in administration of any treatment or procedure, including administration of thrombolytic medications for stroke, should this be the ED provider's management decision.** Since testing will all happen 'in situ' within the ED, there will be no delays associated with patient transport. Likewise, since we will only recruit during shifts when SCs are stationed in the ED, there will be no delays incurred related to SC notification or travel prior to assessing the patient as part of the study protocol.

Another theoretical risk is that care will be delayed because the VOG test results are part of the diagnostic process for VOG care. The total testing time for pre-randomization screening is expected to be about 30-45 minutes, but this will occur 'around' the usual ED care by physicians, providers and nurses, as described in the prior paragraph. The VOG component of the testing will take approximately 20 minutes continuously, but could be interrupted for clinical care. In other words, **VOG care will not lengthen the time of an ED provider's initial assessment or management, or delay its onset.** The VOG diagnosis may identify a stroke missed by

the clinician. In such cases, VOG could speed identification of stroke (i.e., relative to waiting for neurology consultation or neuroimaging), shortening (not lengthening) the time to early stroke therapies.

7. III. Risks of VOG with HIT

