With wrong diagnosis (especially benign vestibular disorders erroneously pursued for stroke), over-testing (especially neuroimaging or admission), confers special risks, described further below.

- The risks of undergoing unnecessary CT will be far higher in the standard care arm than in the VOG-guided care arm (since CT will not be a recommended strategy in any of the VOG clinical pathways).
- The risks of undergoing unnecessary MRI are probably slightly higher in the VOG arm, since the decision rules (algorithm will be used and modified as needed) are tuned to err on the side of not missing a stroke.
- The risks of unnecessary admission are probably slightly higher in the standard care arm.

Patients with benign inner ear disorders are at risk of being harmed by overtesting or overtreatment in pursuit of a stroke or other neurologic diagnosis.

- CT neuroimaging is ineffective, but frequently ordered in routine care for dizziness: The fraction of ED dizziness patients undergoing neuroimaging to rule out stroke or other central causes has risen steadily from 10% in 1995 to nearly 50% in 2015,¹²³ and this includes overuse in patients diagnosed with both BPPV and vestibular neuritis.⁴ Across the US, ED neuroimaging for these patients is still primarily by CT (~47%) rather than MRI (~3%),¹²³ despite the known pitfalls of relying on CT to ‘rule out’ ischemic stroke in the posterior cranial fossa.^{11,17,135} The general increase in neuroimaging over time has not led to a corresponding increase in diagnosis of strokes or other important central causes.²⁷ The same is true for unwanted, wide (1.5-fold), local-area practice variations in ED neuroimaging.¹⁵²
- CT carries meaningful risks: In addition to delays in care, CT risks cancer from radiation exposure¹⁵³ and, if contrast is used, systemic allergy (including risk of death from anaphylaxis)¹⁵⁴ or contrast nephropathy.¹⁵⁵
- MRI carries some risks: *described above in 7. IV. Risks of MRI testing*
- Unnecessary admission carries some risks: Some patients may be admitted to the hospital and unnecessarily exposed to hospital-acquired infections or treated erroneously with medications that have potential side effects or toxicity.^{116,118}

7. VII. Risks of Medicolegal Liability for ED providers

We are sensitive to this issue, but we believe medicolegal risks arising directly from the study are very low.

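### The Aim 2 cost outcome removes off-pathway tests ordered by ED providers from the VRT arm only, so the recorded mean cost difference can move only toward a VRT saving

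*SAP*

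**What the plan says.** SAP 2.2.2 and Protocol 9.2.2 define the outcome in the same words: total dollar cost of tests and consultations obtained during the index visit and, for those admitted, the index admission. Two items are then taken out of the VRT arm's cost: protocol safety MRIs, and "any tests not specified by the pathway but ordered for clinical purposes by ED providers". Tests ordered by consultants or ED providers in the equivocal pathway are kept. Nothing is taken out of SOC, where Protocol 5.1.2 leaves all diagnostic decisions to the treating ED provider. Means are compared by an unequal-variance t-test, with a Wilcoxon-Mann-Whitney test alongside.

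Other sections bear on what the rule deletes:

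- Protocol 5.1.2 lets VRT-arm ED providers "intervene to deviate from VRT pathway if they are concerned about safety for patients in the VOG arm". It adds that these provider roles are the ones expected if the device were used in practice.
- On sequence, Protocol 5.1.2 says: "patient approached for consent as early as possible during ED visit; randomization occurs after VOG testing". Protocol 7.II says "clinical care needs will always take precedence over our research investigations", with usual ED care continuing around 30 to 45 minutes of screening.
- Protocol 7.VI says "CT will not be a recommended strategy in any of the VOG clinical pathways".
- Protocol 6.3.18 says: "VOG care patients slated for discharge will undergo same-day safety MRI if they have not had a clinical MRI".

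The cost result is also part of the second route to Phase 3 (SAP 2.3, Protocol 9.3): accuracy statistically equivalent and costs lower for VRT.

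**The concern.** A randomized cost comparison should count the same things in both arms. Here an ED-ordered CT is charged if the patient is in SOC. If the patient is in the peripheral or central VRT pathway, the same CT can be dropped as off-pathway. A VRT cost close to the pathway as specified is thus set against SOC ordering as it happened.

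Two kinds of test are plainly exposed. The first is off-pathway tests ordered after the VRT report. The second is tests ordered before randomization. Those are balanced between arms in expectation, and the report can neither have caused nor prevented them, yet they can be deleted in one arm only.

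Clinical MRIs in the peripheral pathway are a third, unclear case. Table 1 of Protocol 5.1.2 lists same-day MRI as pathway-required in all three VRT groups. The footnote to the Protocol 6.1 schedule calls it a pathway MRI in the central group and a safety MRI in the other two, unless ordered clinically. A clinical MRI filling that slot could be counted or deleted, depending on which passage governs.

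At stake are the credibility of the Aim 2 result and, in some circumstances, the Phase 3 decision.

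**Working it through.** **The plan's own figure.** Aim 2 has no sample size, unit price, SD or expected difference. The only sizing figure is 113 per arm for Aim 1 (90% vs 75%, alpha 0.05, power 80%). It reproduces with a two-sided test and continuity correction: uncorrected n = (1.96√(2×0.825×0.175) + 0.842√(0.09+0.1875))² / 0.15² = 99.5, or 100; corrected n = (99.5/4)(1+√(1+4/(99.5×0.15)))² = 112.5, or 113. I use 113 per arm below.

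**Direction.** Recorded VRT mean = true VRT mean − Σ(rate of deleted service × unit price). Rates and prices are non-negative and SOC is untouched, so the shift in VRT minus SOC is zero or negative. It is zero only if no such test is ordered.

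**Illustration of size.** Costs are in units of one CT price.

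- From the documents: the national ED CT rate in dizziness, p = 0.47 (Protocol 7.VI), used for SOC.
- Assumed: VRT CT rate r; equivocal share E = 0.2; SD of all other costs s = 1, 2, 3, 5; equal true total costs. When r < 0.47, VRT's other costs are raised by 0.47 − r to keep totals equal. All CTs outside the equivocal pathway are treated as deleted.
- Shift = r(1−E).
- SE = √{[p(1−p) + s² + rE(1−rE) + s²]/113}.
- P(significant false saving) = Φ(shift/SE − 1.96).

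Worked case, r = 0.47 and s = 1: shift = 0.47×0.8 = 0.376; SE = √[(0.249+1+0.085+1)/113] = 0.144; Φ(2.616−1.96) = 0.744.

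| r | Shift | s=1 | s=2 | s=3 | s=5 |
|---|---|---|---|---|---|
| 0.10 | 0.080 | 0.081 | 0.048 | 0.039 | 0.033 |
| 0.235 | 0.188 | 0.261 | 0.103 | 0.068 | 0.047 |
| 0.47 | 0.376 | 0.744 | 0.282 | 0.152 | 0.081 |

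The nominal value is 0.025. The 47% row is not a maximum: with E = 0 and s = 1 the shift is 0.47 and the probability 0.915.

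**Full adherence after the report.** Suppose no VRT patient has a CT after the report, but an assumed share f of the 47% is ordered before randomization. Deleted = 0.47×f×0.8. At f = 0.25 that is 0.094: the true CT saving is 0.47×0.75 = 0.3525 and the recorded saving 0.4465, 27% too large. At f = 0.10 they are 0.423 and 0.4606, 9% too large. Adherence alone does not remove the problem.

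**Phase 3 rule.** I read statistically equivalent as not significantly different, which the documents do not state. By exact enumeration at 75% accuracy in both arms, P(VRT point estimate higher) = 0.469 and P(not higher, not significant) = 0.506. With unbiased equal costs, P(proceed) = 0.469 + 0.5×0.506 = 0.722. With r = 0.10, P(recorded cost lower) is 0.714 (s=1) to 0.548 (s=5), giving 0.830 to 0.746. With r = 0.47 it is 0.996 to 0.713, giving 0.973 to 0.830. At 80% vs 75%, unbiased is 0.896 and r = 0.10 gives 0.940 to 0.906. At 90% vs 75%, the accuracy route alone succeeds with probability about 0.998.

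**The case against.** The best defence is that the rule is deliberate and disclosed. Hypothesis 2 speaks of the VRT pathway, Protocol 9.1 describes a Phase II per-protocol test of potential efficacy, and SOC has no pathway from which a mirror exclusion could be built. That explains the rule but does not make the comparison like for like. Protocol 5.1.2 treats provider deviation as part of expected clinical use. For Aim 1, Protocol 9.1 scores the VRT-based care actually delivered, in order to stay aligned with the randomized design. Tests ordered before randomization belong to neither arm's strategy.

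Several limits do stand:

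- Protocol 7.VI expects that "The risks of undergoing unnecessary CT will be far higher in the standard care arm than in the VOG-guided care arm". Lower VRT ordering makes the bias smaller, as the table shows.
- The clause covers tests ordered by ED providers. A reader might infer that consultations, or tests ordered by consultants or inpatient teams, are deleted too; the text does not expressly say so. The central pathway asks for admission for further evaluation and testing, so some tests there may count as specified.
- A reader might infer that every clinical MRI in the peripheral pathway is deleted. Table 1 does not support that; the point is unresolved.
- A reader might infer that recorded VRT cost must come out below SOC. It need not: required neurology consultations and the central-pathway MRI are counted.

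**Conclusion.** The asymmetry is in the text of both documents, and its direction follows by arithmetic: the mean difference can shift only toward Hypothesis 2. This is certain for the mean; the t-test p-value also depends on the changed variance.

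The size cannot be derived from the documents, which give no prices, cost SD, equivocal share or off-pathway ordering rate; the 47% CT rate is national, not from the trial sites. The 3% to 74% range in the table is a set of scenarios, not bounds.

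A reader might infer that the flaw decides whether Phase 3 proceeds. The documents do not support that. Aim 2 is not the powered endpoint, and at the design accuracies the first route almost always suffices. The cost input matters mainly if VRT is not clearly more accurate, and then a route that asks only for lower costs is sensitive even to a small shift. The rule should be corrected, but the Aim 1 comparison is unaffected.

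**What to change.** In both the SAP (2.2.2 and the decision rule in 2.3) and the protocol (9.2.2 and 9.3):

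1. Make the primary cost comparison, and the cost input to the Phase 3 rule, the cost of all tracked diagnostic tests and consultations at the index visit and index admission in both arms, whoever ordered them and whether before or after randomization.
2. Exclude only MRIs done solely as research safety scans. Reconcile Table 1 of Protocol 5.1.2 with the Protocol 6.1 footnote so that one definition of safety MRI governs costing.
3. Keep the pathway-only costing as a labelled secondary analysis.

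No new data collection appears necessary: Protocol 6.3.24 already records imaging, consultations and admissions without limiting this to one arm. The cost is a wording change in two documents, including a protocol change to a primary outcome, and an estimated saving that is likely to be smaller.
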